1.0 PRECIS

This protocol is a randomized, double blind, placebo controlled trial designed to study the effects of the lipid lowering statin, atorvastatin on HIV-1 viremia.

Untreated HIV-1 infection results in an incurable, progressive immunodeficiency and death, usually from opportunistic infections. Combination antiretroviral therapy (ARV) has been successful in suppressing HIV replication and reducing morbidity and mortality. [1] Long term ARV therapy is associated with the development of HIV-1 drug resistance, and significant adverse side effects including metabolic and cardiovascular complications. [2] Prolonged therapy with certain antiretrovirals is associated with increased risk of cardiovascular disease and a number of dyslipidemic syndromes, including increased levels of cholesterol, LDL, and triglycerides in peripheral blood. [3] New therapeutic strategies to suppress HIV-1 infection are essential.

Previously, in vitro studies suggested that exposure to cholesterol-lowering statins results in decreases in HIV-1 replication.[4, 5] The mechanisms of inhibition remain uncertain, but possibilities include disrupting membrane trafficking or cytoskeletal processes necessary for intracellular transport of viral proteins, or altering cellular activation state necessary for viral gene expression.[4-8] Initial in vivo studies of the effects of statins on HIV-1 have been largely anecdotal in nature and have yielded conflicting results. [9-12] Although statin therapy is commonly used in HIV-1 infection, adverse effects from the combination of antiretrovirals and statins are possible.[13] A more thorough understanding of the effects of statins on HIV-1 replication is essential to determine the potential therapeutic effect and to investigate the risks and benefits of this approach in vivo.

We plan to conduct a double blind randomized placebo controlled trial, with a cross over design, to study the effects of atorvastatin in 22 HIV-infected patients not currently taking antiretroviral therapy. Patients will be randomized to receive either placebo or atorvastatin 80mg for 8 weeks. After a 4 week wash out period patients on the atorvastatin arm will crossover to placebo and vice versa patients in the placebo arm will cross over to atorvastatin for an additional 8 weeks. Upon completion of study medications all patients will be followed for 4 weeks. Each arm will have a minimum of 11 patients each. The primary outcome measure in this study is the effect of lipid lowering agents on HIV-1 RNA levels; additional secondary outcome

measures include effects of lipid lowering agents on lipid profile, markers of inflammation and immune activation and investigations of host and viral genetic factors.

2.0 BACKGROUND

2.1 HIV structure and replication

HIV-1 is a member of the lentivirus family of retroviruses, a group of enveloped RNA viruses that replicate via a DNA intermediate. The HIV genome is composed of genes that code for structural components, enzymes necessary for viral replication, as well as regulatory and accessory proteins. Steps in HIV-1 replication depicted in figure 1 include viral binding and interaction with chemokine receptors (1), membrane fusion, (2) viral uncoating (3) and reverse transcription of viral RNA (4). The pre-integration complex is then transported to the nucleus where viral DNA integrates into the host cell chromosome (5) followed by viral RNA synthesis (6). The later steps include translation of viral mRNA into viral proteins, virion processing, assembly, (7) maturation followed by budding and release (8).

[figure not shown]

Figure 1 - Schematic representation of HIV-1 replication (adapted from the article by Peterlin and Trono [14])

2.2- Potential antiretroviral targets

Initially, antiretroviral therapy was concentrated exclusively on viral targets and focused on available inhibitors of viral enzymes reverse transcriptase and protease (Steps 4, and 7, respectively) or the viral fusion reaction (Step 1). Newer approaches include targeting interactions between host and viral factors, including inhibiting virion binding to susceptible cells with HIV-1 coreceptor inhibitors.[15] HIV populations in vivo are genetically diverse, and one effect of drug therapy is selection of viral mutants that are resistant to antiretrovirals. Emergence of drug resistance is one of the most critical factors limiting long term suppression of HIV replication. New therapeutic strategies to limit HIV replication are essential. One such approach is to target cellular processes that are essential for virus replication in such a way that virus replication is inhibited without causing critical damage to cellular functions. In one potential example of this approach, several investigators have reported that statin therapy may inhibit HIV-1 replication in vitro, either by interfering with intracellular transport or cellular activation pathways, resulting in marked reductions in HIV replication without significant cellular injury.[4-8] In vivo data evaluating this approach are lacking, and we propose to investigate the effects of statin therapy on HIV-1 replication in chronically infected individuals.

2.3 Host and viral factors in HIV assembly, budding and release

HIV virion maturation is a complex process requiring interactions between the host and the virus. One critical step in virus replication, virion assembly, requires specific host virion interactions. Virion components are transported to the cell surface using specific lipid “rafts”, cholesterol-rich cellular micro domains and bud through cell membranes by co-opting the multivesicular body (MVB) process that normally functions to recycle plasma membrane components.[16] [17] Transport via rafts is a highly specialized process that requires specific protein protein interactions; for HIV-1 transport is thought to involve both cellular and viral gene products.

Host pathways involved in transport and budding include a series of membrane- protein complexes which bind target proteins and ensure targeting to specific intracellular locations. A number of cellular proteins have been identified that participate in intracellular trafficking, including TSG101, a lipid raft constituent, which binds specific protein domains ensuring transport.


2.4- Statins and their putative effects on viral replication and T cell activation

Disruption of lipid rafts may not be the only mechanism by which statins might alter viral replication. Statin drugs are competitive inhibitors of the enzyme HMG CoA reductase. This enzyme catalyzes the conversion of HMG CoA (3-hydroxy 3 methylglutaryl-coenzymeA) to mevalonate, the rate limiting step in cholesterol synthesis. By limiting synthesis of mevalonate, statins inhibit the synthesis of not just cholesterol but also of non-steroidal isoprenoid derivatives. Non-steroidal isoprenoid compounds are involved in the post-translational modification of several cell proteins including the Rho and Rac GTPases.

The Rho family of GTPases, this family includes Rac GTPases, control actin cytoskeleton remodeling in response to stimuli.[28] HIV entry into cells is an actin dependent process.[6] It is believed that interactions between HIV *env*, CD4, and its co receptors activate Rac-1 GTPase. This stimulates actin filament reorganization, which is needed for HIV fusion.[7] By blocking mevalonate synthesis, statins prevent the functioning of Rho GTPases and actin cytoskeleton remodeling. [29] Recently published data suggest that by targeting the function of Rho GTPases statins inhibit HIV-infection of SCID mice grafted with adult human PBMCs.[11]

T cell activation plays an important role in HIV progression. Depletion of CD4 positive cells during HIV infection is not merely a consequence of direct infection of these cells. T cell activation leads to T cell proliferation T cell depletion and ensuing immunosuppression. [30] Statins alter T cell activation and may affect disease progression in HIV infected patients. Statins may affect T cell activation via several mechanisms including altering MHC II expression and lipid rafts disruption. T cell receptors localize within lipid rafts and disruption of lipid rafts leads to altered T cell activation. [31] [32]

2.5 Statin effects on HIV-1 RNA levels *in vivo*

In vivo data on statin use in HIV infection is limited. In a study of 6 early stage (CDC stage A1), ARV naïve patients with stable viral loads, treated with lovastatin, plasma viral load decreased with statin use. The reductions in viral load in this group of patients were between 0.2 and 1.3 log₁₀ copies. Viral loads done 12 weeks after Lovastatin discontinuation demonstrated a viral rebound, with 5 of the 6 patients demonstrating a change in their set point. This study was non-randomized and did not study viral RNA levels in patients not treated with statins[11]. In a recent report, we reported analysis of patients treated with 40 mg Pravastatin as part of a study of

endothelial function. Seven patients in this study had detectable viremia allowing the authors to analyze the effects of Pravastatin 40 mg on viral load. 3/7 patients had a decrease in viral load while 4/7 had increases. We concluded that there appeared to be no significant effect of statin therapy on HIV-1 viral RNA levels in this group. Interestingly, however, 3/7 patients had rebound in viral load after discontinuation of Pravastatin.[12] Two additional studies have also failed to show any effect of statin therapy on HIV-1 viral RNA levels. In a retrospective study patients who started “first line HAART” were compared with those who started ‘first line HAART” and were at some point thereafter started on statins. In this study the 2 groups did not differ in the number of patients who had viral rebound after initial suppression to less than 500 copies/ml or blips (defined in this study as a decline in viral load to <500 copies followed by a rebound to greater than 500 copies/ml and then a fall to <500 copies).[10] Finally, chronically infected patients who had discontinued antiviral therapy for 12 weeks were studied by examining the effects of Simvastatin (80mg) on HIV-1 RNA. No decreases in viral RNA were detected after 4, 8 and 12 weeks.[9] The results of this study are difficult to interpret given the missing data points.

There may be numerous reasons for the inconsistent effect of statin exposure on HIV-1 viral RNA levels; statins may be effective with certain strains of HIV-1 or with specific combinations of TSG101/p6 genotypes. Effects may not be manifest or may be blunted in patients with elevated cholesterol levels at baseline, where statin induced decreases may not sufficiently decrease intracellular cholesterol levels sufficiently to affect HIV replication. The lack of a rigorous study design for most of these studies may introduce sufficient bias to prevent clear cut results.

The 3 statins tested thus far in vivo models are pravastatin, lovastatin and simvastatin. Pravastatin is the only statin that does not have significant drug- drug interactions in HIV positive patients on antiretrovirals. However, pravastatin use is associated with modest decreases in serum cholesterol, as the decreases in serum cholesterol seen with pravastatin use may not be sufficient to result in lipid raft disruptions necessary to demonstrate any significant antiviral effects. Both simvastatin and lovastatin use is associated with significant decreases in serum cholesterol but both drugs are contraindicated with other antiretrovirals. Atorvastatin use is associated with significant reductions in serum cholesterol, and several reports suggest that the

use of atorvastatin while theoretically contraindicated with antiretrovirals is safe and well tolerated. Given this we chose to study atorvastatin for its antiviral effects.

To further define the effects of statins on HIV viremia and to study virus host interactions in the context of statin use we have designed a randomized placebo controlled cross over study of atorvastatin use in HIV positive patients. In this study the effects of cholesterol reduction on HIV-1 viremia, T cell activation, and metabolic parameters in HIV positive patients will be explored. Furthermore viral and host genetic factors as it relates to response or lack of response to statins will also be explored.

3.0 OBJECTIVES

3.1 Primary objective

The primary objective of this study is to compare the changes in HIV-1 viral load during the atorvastatin phase with the changes in viral load in the placebo phase.

3.2 Secondary objectives

- To compare the changes in the expression of immune activation markers between the placebo phase and the atorvastatin phase.
- To investigate HIV-1 and TSG 101 phenotypes among enrollees
- To investigate the changes in the metabolic profile between the placebo and the atorvastatin phase
- To investigate the safety profile of atorvastatin in HIV positive patients not on antiretroviral therapy
- To compare the subjective and objective evaluation of fatigue during the atorvastatin and placebo phase

4.0 STUDY DESIGN

Study design

This study utilizes a case cross over design to investigate the effects of atorvastatin on HIV viral load, immune activation markers and metabolic profile. Figure 2 is a diagrammatic representation of the study design. A double blind strategy was chosen for the design of this trial. In general statin therapy is associated with a number of side effects, some of which, including

fatigue and muscle aches may be highly subjective or multifactorial in origin. If statins do show an antiviral effect, then their use will be balanced by well described adverse effects. We wish to evaluate such adverse effects in detail in patients enrolled in the trial, and feel double blind approach is the most rigorous and objective.

HIV positive patients, who have been off anti-retroviral medications for a minimum of 3 months and with no documented evidence of resistance, will be recruited for this study. Each subject will have 3 baseline viral loads and will be randomized to receive either 80 mg of atorvastatin or placebo for 8 weeks. Following this, there will be a 4 week wash out phase. Upon completion of the wash out phase patients who were initially on the atorvastatin arm will switch to the placebo arm, while patients who started in the placebo arm will switch to atorvastatin to complete an additional 8 weeks. All patients will be followed for 4 more weeks upon completion of study medications. The study design is schematically represented in Figure 2.

[figure not shown]

Figure 2 - Graphical representation of the study design (time represented in weeks)

5.0 SELECTION AND ENROLLMENT OF SUBJECTS

5.1 Inclusion Criteria

Establish with patient prior to Informed Consent:

- Adults 18 years of age or older
- HIV-1 infection, as documented by a licensed ELISA test kit and confirmed by a Western blot assay at any time point prior to study entry or at study entry (May do after informed consent if no test results are available).

Off all ARV for \geq three months prior to study entry, no documented evidence of viral resistance, and no evidence of acute HIV infection. For the purposes of this study acute HIV infection will be defined as presence of a detectable HIV-1 viral RNA in the presence of a non reactive HIV-1 or HIV-2 antibody assay or an indeterminate western blot. For the purposes of this study viral resistance is being defined as having a genotypic or phenotypic evidence of resistance or in the absence of formal resistance testing clinical evidence of resistance for e.g. patients with persistent viremia in the face of adequate adherence

- Willingness to use a method of contraception during the study period. Adequate methods of birth control include: condoms, male or female, with or without a spermicide; diaphragm or cervical cap with spermicide; intrauterine device; any of the methods that require a prescription (such as contraceptive pills or patch, Norplant, Depo-Provera, and others) or a male partner who has previously undergone a vasectomy,
- Willingness to have blood drawn
- Non known allergy or contraindication to atorvastatin use
- Ability to understand and willingness to sign the informed consent
- Willingness to have blood stored for future phenotyping and genotyping

After Informed Consent:

- CD4 cell count greater than 350 cells/ml
- 3 viral loads that average greater than 1000 copies/ml within a 4 week period.
- The viral loads will be done using the bDNA method in the NIH laboratory and must be within 20% (log10bDNA of each other).
- A fasting total cholesterol lower than 240mg/dl and a LDL cholesterol lower than 130mg/dl
- Liver function tests (AST or ALT) not greater than 1.5 times the upper limit of normal. Evidence of active hepatitis B or C will not be considered an exclusion criteria if the liver function tests are within normal limits.

- Creatine phosphokinase elevations (CPK) not greater than 3 times the upper limit of normal (ULN) on two sequential determinations and, in the opinion of the investigator, without clear association with exercise.
- Laboratory values:
 - Absolute neutrophil count (ANC) $\geq 1000/\text{mm}^3$.
 - Hemoglobin $\geq 11.0 \text{ g/dL}$.
 - Platelet count $\geq 100,000/\text{mm}^3$
 - Creatinine $\leq 2 \times \text{ULN}$
 - Serum amylase and lipase $\leq 1.25 \times \text{ULN}$
- Negative serum pregnancy test at randomization

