- Patient develops any condition that the study investigators deem would be detrimental for the patient to continue on the study
- If the patient desires to leave the study
- Patient starts taking other lipid lowering drugs including fibric acid derivatives, bile acid sequestrants and niacin preparations
- Patients will be dropped from the study if their CD4 count drops by fifty percent on two successive determinations, or falls below 250 cells/ μ l in the absence of any documented ongoing infections/inflammatory processes while on study

If subjects are discontinued from the study secondary to any of the above given reasons they will be replaced according to the prior randomization.

CLINICAL AND LABORATORY EVALUATION

Evaluation*	Screening	Randomization	D7 W1	D14 W2	D42 W6	D56 W8	D84† W12	D91 W13	D98 W14	D126 W18	D140 † W20	D168 W24
Documentation of HIV	Pos ELISA and Confirmatory Blot, previous results will be allowed											
Medical /Medication history	✓	✓	✓	✓	✓	✓	✓	✓	✓	✓	✓	✓
Nadir CD4	✓											
Clinical Assessment	✓	✓	✓	✓	✓	✓	✓	✓	✓	✓	✓	✓
Questionnaires		✓				✓	✓				✓	✓
Physical Exam	✓	✓				✓	✓				✓	✓
Hepatitis profile	✓											
Fasting lipid profile	✓	✓	✓			✓	✓	✓			✓	✓
Markers of inflammation		✓	✓			✓	✓	✓			✓	✓
Hematology	✓	✓		✓	✓	✓	✓		✓	✓	✓	✓
Chemistry including CK	✓	✓		✓	✓	✓	✓		✓	✓	✓	✓
Liver Function Tests	✓	✓		✓	✓	✓	✓		✓	✓	✓	✓
Urinalysis	✓	✓				✓	✓				✓	
Pregnancy Testing	✓	✓	✓	✓	✓	✓	✓	✓	✓	✓	✓	✓
Full FACs	✓	✓	✓			✓	✓	✓			✓	✓
HIV viral load (bdna)	✓ (3 viral load measures will be used to establish baseline)	✓	✓	✓	✓	✓	✓	✓	✓	✓	✓	✓
Statin/placebo		✓	✓	✓	✓	✓	✓	✓	✓	✓	✓	
Stored Plasma/PBMC		✓	✓	✓	✓	✓	✓	✓	✓	✓	✓	✓
Stored Sera		✓				✓	✓				✓	

- * Study consent will be signed at NNMC prior to screening and at randomization at the NIH
- † In the event subject is vaccinated these visits will be extended by 2 weeks

Table 1- Schedule of events

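### The CD4 entry limit in 5.1 is written per ml and the CD4 withdrawal limit in 5.4 per µl, so as written the entry limit lies below the withdrawal limit

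*Combined protocol and SAP*

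**What the plan says.** Section 5.1, in the criteria checked after informed consent, sets the entry limit: "CD4 cell count greater than 350 cells/ml".

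The discontinuation list in section 5.4 sets two CD4 rules. The relative rule reads "Patients will be dropped from the study if their CD4 count drops by fifty percent on two successive determinations". The absolute rule applies if the count "falls below 250 cells/ μ l in the absence of any documented ongoing infections/inflammatory processes while on study". Of subjects discontinued for any listed reason, the section says "they will be replaced according to the prior randomization".

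The 350 and the 250 are the only absolute CD4 limits in the document. No other section defines or corrects the entry unit. In the same eligibility list, the neutrophil and platelet limits are given per mm³, and the viral load criterion that follows the CD4 line is in copies per ml.

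**The concern.** The two limits apply to the same laboratory value but use volume units that differ 1000-fold. An entry limit should lie at or above the level at which a patient is removed. As written, it lies far below.

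This is an operative threshold, not background text. Participants must be off all antiretroviral drugs, follow-up runs to week 24 (8 + 4 + 8 + 4 weeks), and the CD4 line is the only numeric limit on immune status at entry. A checklist, case report form or monitor that copied the criterion as it stands would accept nearly any count. A patient could then enter below the level at which section 5.4 would remove someone, in a trial of only 22 patients that replaces those it discontinues.

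**Working it through.** **Inputs**

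- Entry limit: more than 350 per ml (5.1).
- Absolute withdrawal limit: below 250 per µl (5.4).
- Other cell counts in the 5.1 list: neutrophils at least 1000/mm³, platelets at least 100,000/mm³.
- Conversions: 1 ml = 1000 µl; 1 mm³ = 1 µl.

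**Step 1. Put both CD4 limits in one unit.**

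| Limit | As written | Per µl | Per ml |
|---|---|---|---|
| Entry (5.1) | > 350 per ml | 350 / 1000 = 0.35 | 350 |
| Withdrawal (5.4) | < 250 per µl | 250 | 250 × 1000 = 250,000 |

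Ratio of withdrawal limit to entry limit as written: 250 / 0.35 = 714. This is smaller than the unit factor of 1000 because the two numbers also differ (1000 × 250 / 350 = 714).

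**Step 2. See which patients the literal criterion treats oddly.**

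- At or below 0.35 cells/µl: excluded. Almost nobody is in this range.
- Above 0.35 and below 250 cells/µl: eligible under 5.1, yet already below the 5.4 limit. This is where the two sections conflict.
- From 250 to 350 cells/µl: eligible as written, but not eligible if the entry limit were per µl. There is no conflict with 5.4.
- Above 350 cells/µl: eligible on either reading.

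**Step 3. Try a common unit.** If both limits are per µl, entry is above 350 and withdrawal below 250: a ratio of 350 / 250 = 1.4 and a gap of 100 cells/µl. The order is then coherent.

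**Step 4. Look for evidence of which unit slipped.** The neutrophil and platelet limits are per mm³, that is, per µl. The CD4 line is the only cell count in the list given per ml, and the viral load line after it is properly per ml. This points to the unit in 5.1, but it is an inference.

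**Step 5. Check whether any statistic moves.** The plan states no figure that uses the CD4 limit. The power statement in section 7.0 rests on an SD of 0.74, a correlation of 0.75 and 20 subjects:

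- SD of the paired difference = 0.74 × √(2 × (1 − 0.75)) = 0.523.
- Noncentrality = d / (0.523 / √20), with 19 degrees of freedom and two-sided 0.05.
- Power is 77.1%, 90.0% and 98.2% for d = 1/3, 0.4 and 0.5 log₁₀, against the stated 77%, 90% and 98%.

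The stated power reproduces, and no CD4 value enters it.

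**The case against.** The strongest case against is that this is a one-character slip that any HIV clinician would correct on sight. Section 5.3 leaves patient identification to health care providers at the sites, and at one site to infectious disease clinic staff, with the investigator or a designee going through the protocol with candidates. Other provisions also limit the risk. Section 5.2 excludes certain active infections and recent serious illness. Section 5.4 allows discontinuation when antiretroviral treatment is needed, and has the relative CD4 rule. This stands as a limit on practical weight. It does not correct the unit, and none of these provisions sets a CD4 level for a patient who is otherwise well.

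A misread character in the PDF text cannot be fully excluded either, since the difference is µ against m. It is unlikely: the micro sign came through in 5.4, and the unit in 5.1 is clean. A look at the source page settles it.

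A reader might go further and infer that anyone enrolled under the literal criterion would be withdrawn at the first on-study count and replaced. The documents do not support that. A patient at 300 or 600 cells/µl also meets the literal criterion and is not below 250. Even for a patient under 250, the rule is worded as a fall below the limit, and it excepts patients with infection or inflammation on record. Early withdrawal is possible for that group, but not automatic.

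A reader might also infer that patients with advanced immunodeficiency would in fact be enrolled, or that the trial's power is affected. Nothing in the documents shows the first, and the check of section 7.0 rules out the second as far as the stated calculation goes.

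**Conclusion.** The point holds as an error in eligibility wording. As written, the entry limit is 0.35 cells/µl, about 714 times below the withdrawal limit. It screens out almost nobody and admits patients who are already below the level at which 5.4 would drop them. The two sections cannot both stand as written.

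That the slip lies in the 5.1 unit is the most likely explanation, given the units in the rest of the list. What the documents prove is only that the two units disagree. Which numbers and unit apply is for the sponsor to confirm.

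The practical weight is modest. Sample size, power and analysis are unchanged, and harm would need someone to apply the literal unit. The correction is still warranted, because an eligibility threshold should not rely on readers to repair it silently. The conclusion assumes that the unit in 5.1 was read correctly from the source page.

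**What to change.** Reconcile the CD4 entry limit in 5.1 and the CD4 withdrawal limit in 5.4 to one volume unit, with the sponsor confirming both numbers. Carry the confirmed unit to the eligibility checklist and the case report form. Check the source page of 5.1 first; if it already reads per µl, the point closes.

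The cost is one unit in a protocol amendment and the matching change on the forms. Design, sample size and analysis stay as they are.
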